## Descriptive Evaluation Analysis Plan

### The Evaluation of the Family Champions Project in Dallas, TX

#### A. Description of the intended intervention(s)

Anthem Strong Families' Family Champions Project (FCP) offers skill-building primary curriculum and support services to program participants. The evidence-based TYRO Leadership and TYRO Core Communication curricula, totaling 18 hours, are offered as group classes by trained facilitators in which low-income adults learn skills related to healthy relationships and financial wellbeing. Support services, including case management and additional, optional classes through Anthem's Mini-Clinic series, are available to all FCP participants.

The main intervention being tested in this descriptive evaluation is the multistep continuous quality improvement (CQI) cycle created by Midwest Evaluation and Research (MER) that aims to improve FCP program implementation. The content and components of each step in the process are described below.

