#### 2. **Step 2: Performance Intervention Priorities Report (prepared and presented annually in quarter 2 of each grant year by evaluation lead)**

- a. Report description – compare overall performance trends by service site
- b. Purpose – target improvement efforts by setting site-specific priorities for interventions
- c. Fidelity tracking -
  - i. Intended amount of CQI to be offered based on intended report timeline
  - ii. Actual amount offered (# CQI Team meetings scheduled for Step 2 Reports on Outlook, # CQI Team meetings where Step 2 CQI Report was presented to CQI Team, # Step 2 reports created)

---

- d. Dosage tracking –
  - i. Intended amount received – attendance of all members at CQI Team meetings for Step 2 Reports (i.e., number, names, roles)
  - ii. Actual amount received – CQI Tracking Sheet for Team Attendance (See Appendix B) for Step 2 Reports
- e. Feasibility Assessment –
  - i. Focus on utility and user-friendliness of Step 2 report
  - ii. CQI Team Survey for Step 2: administered each program year to staff on the CQI Team
  - iii. Family Champions Project staff survey for Step 2: administered each program year to all frontline staff who help to develop targeted, site-specific interventions during staff meetings with leadership and with the CQI team on a rotating basis

**3. Step 3: Performance Intervention Strategy Report (prepared for each service site in quarter 2 of each grant year by evaluation lead)**

- a. Report description – use key indicators to track performance trends for each site individually
- b. Purpose – establish a performance intervention agenda for each site
- c. Fidelity tracking –
  - i. Intended amount to be offered based on intended report timeline
  - ii. Actual amount offered (# CQI Team meetings scheduled on Outlook, # CQI Team meetings where Step 3 CQI Report presented to CQI Team, # Step 3 reports created)
- d. Dosage tracking –
  - i. Intended amount received – attendance of all members at CQI Team meetings for Step 3 Reports (i.e., number, names, roles)
  - ii. Actual amount received – CQI Tracking Sheet for Team Attendance for Step 3 Reports
- e. Feasibility assessment –
  - i. Focus on utility and user-friendliness of Step 3 report
  - ii. CQI Team Survey for Step 3: administered each program year to staff on the CQI Team

**4. Step 4: Performance Intervention Results Reports (prepared annually in quarter 4 of each grant year by evaluation lead)**

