CQI Process Step 4	Assessing the results of targeted interventions that were put in place at specific sites based on the findings of the Step 2 and Step 3 reports	Reports are prepared annually in the fourth quarter of each grant year and discussed at standing CQI team meetings	Existing CQI team meetings are used to present and discuss Step 4 report findings (e.g., did the targeted metrics improve after implementing interventions? Does the metric now meet relevant standards? Were there any challenges with the implementation of interventions? How did frontline staff, leadership, and facility staff find the intervention? ); the evaluation lead facilitates the CQI team meetings and presents the Step 4 reports to the CQI team. Program leadership share Step 4 report findings with frontline staff in staff meetings.	CQI team members (program director, program manager, evaluation lead, data manager(s)); program staff (case managers, facilitators, recruitment and retention specialists) who are able to 1) provide feedback on challenges and successes with the implementation of the intended intervention, 2) see the results of the intervention
Relationship skills workshops	Healthy relationships curriculum (TYRO Core Communication; TYRO Leadership)	A total of 18 hours, with six two-hour sessions occurring weekly (TYRO Leadership) plus two three-hour sessions occurring weekly (TYRO Core Communication)	Group lessons provided online via Zoom or in-person at service sites; two trained facilitators lead every session	Individuals in the greater Dallas-Fort Worth area with low income

**Table 2.** Staff education and training (initial and ongoing)

Component	Education and initial training	Ongoing training
Relationship skills workshop	All facilitators, case managers, intake specialists, and other members of the staff must complete the workshop as a participant before entering the certified TYRO Facilitator training component. Once the training is complete, each facilitator observes an experienced staff	Facilitators complete an annual refresher process to ensure curriculum fidelity. That process includes observations by the Program Manager, Program Director, or another qualified designee. We attempt to provide opportunities to become re-certified every two to three years. Other

Component	Education and initial training	Ongoing training

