### 1. Research questions

RQ1.1: Did the multistep CQI process support changes in primary workshop dosage, program attrition rates, or survey response rates at the program level?

RQ2: Did meaningful improvements in primary workshop dosage, survey response rates, or program attrition rates vary by service site *for sites that focused on improving the same metrics?*

RQ3 [secondary]: Do participants report healthier partner relationship attitude outcomes after program participation, as compared to baseline?

RQ4 [secondary]: Was level of dosage associated with reporting healthier partner relationship attitude outcomes after program participation, as compared to baseline?

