#### 4. Outcome measures

The main outcomes of interest addressed by the multistep CQI process are primary workshop dosage, participant attrition rates, and nFORM survey response rates, as these are key program performance metrics with targets set by the federal funders. The first research question looks at changes in each of these metrics over time overall across all service sites (program level), and the second research question looks at changes in each of these metrics over time broken down by service site for sites that focused on the same metrics. This will involve an assessment of any changes in metrics after intervention strategies were implemented, including whether performance targets were reached and whether improvements were meaningfully large. Potential ceiling and floor effects are mitigated during the process of selecting which metrics to attempt to improve via intervention strategies (i.e., metrics that are already at or close to targets are not selected for intervention); however, potential ceiling and floor effects will also be addressed by providing baseline data for metrics targeted for interventions at each service site.

The secondary research questions about participant-level attitude changes after program participation are assessed by constructing a composite measure calculated as the average of five nFORM survey items related to partner trust and intimacy. If more than one survey item within the composite is missing for a respondent, the value of the outcome measure will be set to missing.

**Table 4.** Outcomes used to answer the research questions

Research question	Outcome name	Description of the outcome measure	Source of the measure	Timing of measure
RQ1	Dosage	The outcome measure is the percent of target primary workshop hours received by program participants	nFORM operational report: Primary Workshop Participation Detail	Attendance is recorded after each workshop session
RQ1	Attrition	The outcome measure is the percent of program participants who leave the program without completing at least 90% of primary workshop hours	nFORM operational report: Client Status Summary	Ongoing

Research question	Outcome name	Description of the outcome measure	Source of the measure	Timing of measure

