**Family Champions Project
Statistical Analysis Plan**

Clinicaltrials.gov ID: NCT05298345

September 4, 2024

Analysis approach

To assess the association between the multistep CQI process and the outcome measures, trends in dosage, retention, and survey response rates will be assessed over time since the start of the program. If the CQI process has been effective in identifying and addressing issues that require intervention, we would expect that program implementation would get stronger over time, as measured by progress toward meeting programmatic targets for these measures.

Analytic sample

The analytic sample for RQ1 and RQ2 is made up of the participants who received services at the facilities that received CQI intervention efforts as part of the multistep CQI process. The aggregated dosage, retention, and survey response rate data for these participants will make up the analytic sample.

The analytic sample for the secondary research questions (RQ3 and RQ4) about participant healthy partner relationship attitudes will be defined as participants who have complete baseline and outcome data for the constructed outcome measure (complete case). Because these relationship questions are only shown to participants who report currently being in a romantic relationship, participants can only have complete case survey data if they report being in a relationship at both waves of data collection. As mentioned above, participants will only be included in the analytic sample if they have one or no missing values for the five items used to construct this outcome measure (80% or 100% of non-missing items). Participants who do not meet this threshold will have their outcome value assigned to missing and will not be included in the analytic sample; no imputation is planned for the outcome data.

Data preparation

Program-level and participant-level data will be downloaded as an Excel file using nFORM's data export feature. The data sets will be cleaned and prepared for analysis using the R Studio statistical software package. All files will be exported into R and cleaned separately before data sets are merged into a final, wide format file for analyses using nFORM client ID as the unique identifier for matching programmatic (dosage, client status, survey response rates) and participant survey data.

Analytic approach

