Sample attrition at the participant outcome level will be reported descriptively in the final report. We plan to report the proportion of total program enrollees that is missing for the outcome measure and for what reason (e.g., survey non-response, not eligible to answer relationship questions, exceeded 20% threshold for item missingness within the construct).

Implementation Analysis

Analysis approach

To address these implementation research questions, we will analyze a combination of quantitative and qualitative data. Some quantitative measures of fidelity and engagement will be counts with no calculations required (e.g., number of reports, number of meetings attended, etc.). Engagement measures that use staff survey data will involve simple percentage calculations of the number of responses that rated understandability and feeling welcome as Somewhat Agree or higher, reported descriptively. The sample size of the engagement measures will be the number of survey responses received from the CQI team and broader program staff. Survey responses will be checked for completeness, and we will also ensure that answer levels are numerically coded, and reverse-code where necessary. For the qualitative measures related to context, the evaluation team will summarize broad themes that arise during staff interviews about lessons learned, barriers to implementing CQI, and best practices for the field. The sample size for the context measures will be the number of interviews conducted during site visits. Interview data will be analyzed for key themes by the evaluation lead.

Measures for addressing the implementation research questions

Implementation element	Research question	Measures
Fidelity	To what extent were the five steps of the CQI process carried out as intended each grant year?	
 Total number of reports delivered for each step of the CQI process Timing of report delivery for each report delivered Number of targeted interventions implemented at each service site
Fidelity	What were the unplanned adaptations to key CQI process components?	
 List of unplanned adaptations, such as in report timing or CQI process components cut

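### The SAP's single RQ1/RQ2 sample does not match the Protocol's all-site RQ1, and the crude RQ1 trend can move with site mix alone

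*SAP*

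**What the plan says.** Protocol section B.1 asks in RQ1 whether the CQI process supported changes in dosage, "program attrition rates, or survey response rates at the program level". Section B.4 confirms the scope: the question "looks at changes in each of these metrics over time overall across all service sites (program level"). Only RQ2 carries a site restriction, namely "for sites that focused on improving the same metrics".

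The SAP, under Analytic sample, covers both questions with one sentence: "The analytic sample for RQ1 and RQ2 is made up of the participants who received services at the facilities that received CQI intervention efforts". It does not define what counts as receiving such efforts.

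Under Analytic approach, the SAP plots average dosage, attrition and survey response by month of enrollment, both across sites and by site. Targeted interventions are marked on the graphs, and site averages are compared over the whole study. No fixed set of sites, weighting or site term is given for the cross-site line. Under Analysis approach, the trends have two uses: to judge progress toward program targets, and to assess the association between the CQI process and the outcomes.

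Protocol section B.2 says that service locations changed during the program. It names ten, one of them virtual, and promises participant counts by site in the final report.

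**The concern.** RQ1 is one of the two questions not labelled secondary. Two careful analysts who follow the SAP sentence could include different participants in it. On the narrow reading, the RQ1 result would not describe the program. It would also lean toward sites that began badly, because Protocol section B.4 says that metrics at or near target are not picked for intervention.

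The second issue applies whichever sample is used. When sites with different usual levels enter and leave, their pooled average changes even if no site changes. A reader who takes the RQ1 line as evidence on the CQI process could credit CQI with a change in where people enrolled.

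**Working it through.** **Plan's own figure.** The only figure is the projected enrollment of 800 (Protocol B.2). No rates, SD, effect size or power are given, so it cannot be reproduced. Nothing below depends on how it was chosen.

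**The two readings of the sample.**

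- *Broad: every site is covered.* Protocol section A states: "The main intervention being tested in this descriptive evaluation is the multistep continuous quality improvement (CQI) cycle". Step 3 reports are "prepared for each service site in quarter 2 of each grant year". The SAP itself calls the RQ1 line program-level and cross-site. For site-specific actions it uses a separate term, as in its fidelity measure: "Number of targeted interventions implemented at each service site".
- *Narrow: only sites given a targeted intervention.* Protocol Table 1 describes Step 4 as assessing "targeted interventions that were put in place at specific sites", and section 3 of the implementation study also speaks of interventions at a given site. No text says that every site received one.
- *Virtual services.* Section B.2 lists Zoom among the service locations. Table 1 sets Zoom apart from in-person sites, though only when describing delivery. The SAP says facilities.

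**Effect of omission.** Let s be the share of enrollees omitted, held constant over time. Then restricted change − program change = s × (change at included sites − change at omitted sites). All inputs are assumed, and either sign is possible:

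- s = 0: 0 points
- s = 10%, difference ±5: 0.10 × 5 = ±0.5 points
- s = 20%, difference ±10: 0.20 × 10 = ±2 points
- a 10-point rise at included sites and none at omitted sites: 9, 7 or 5 points program-wide for s = 10%, 30% or 50%

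**Selection on poor earlier metrics (narrow reading).** A simulation used 10 sites with a mean level of 80%, 20 or 40 participants per site per period, and a between-site SD of 0 to 10 points. Sites observed below 80% were selected. With no intervention effect, the selected sites rose by 3.1 to 9.4 points, while all sites together changed by about 0. This is an outer illustration. It compares the period used for selection with the next one on a single metric, whereas a facility could enter the SAP sample through any metric.

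**Site mix.** With two groups of sites at constant levels, change in crude average = (gap in site rates) × (change in enrollment share).

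- gap 10, shift 0.1: 1 point
- gap 20, shift 0.3: 6 points
- sites at 90% and 70%, share of the better site 0.3 to 0.7: 0.3×90 + 0.7×70 = 76, and 0.7×90 + 0.3×70 = 84, so +8
- the same shift with both sites falling by 2 points: 0.7×88 + 0.3×68 = 82, so the crude line still rises by 6
- gaps of 5 to 30 with shifts of 0.1 to 0.6: 0.5 to 18 points

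**Precision of an adjusted trend.** The gap-20, shift-0.3 case was simulated with 800 participants, 6, 10 or 14 locations, classes of 10, class ICC of 0 to 0.10, and no within-site change. With SD 30, the crude trend averaged +5.7 to +6.3 points over the study. The site-fixed-effects trend averaged −0.2 to +0.2, with a standard error of 3.9 to 6.0 (1.96 × SE = 7.6 to 11.8).

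SD 30 suits dosage only. Attrition and survey response are binary: at 85% and 65% the SDs are √(0.85×0.15) = 35.7 and √(0.65×0.35) = 47.7 points. For these the adjusted standard error is roughly 5 to 8.5. The crude trend's own standard error is 5.1 to 6.6 (SD 30) or 6.3 to 8.2 (binary).

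**What the planned site displays can show.** April 22, 2021 to February 15, 2025 is 1395 days, or 45.8 months, and 800/45.8 = 17.5 enrollees per month. If 3, 5 or 10 locations enroll at once, that is 5.8, 3.5 or 1.7 per location-month. The standard error of a location-month mean at SD 30 is then 12.4, 16.1 or 22.7 points. Full-period site averages are much steadier: with 6 to 14 equal sites, 30/√133 = 2.6 to 30/√57 = 4.0 points, ignoring class clustering.

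**The case against.** The broad reading arguably has more support in the text, and on it the omission is exactly zero. No passage says that any site is left out of RQ1. The case for excluding virtual services rests mainly on one word in the SAP. A reader might infer that the SAP does cut RQ1 down to intervention sites; the documents do not support that. What stands is that one undefined sentence cannot express two scopes that the Protocol keeps apart.

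On site mix, the study is descriptive, no test is planned for RQ1, and the crude line answers the question about targets. The plan also has safeguards: site-level trends with interventions marked, the full-period site comparison, participant counts by site, and baseline data for targeted metrics. The full-period comparison shows the gap in site rates, one of the two factors in the mix formula. That credit is due. However, none of these is planned to show each site's share by period, and none adjusts the line. The SAP also states an association aim, for which the crude line is not enough.

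It is also fair that the simulation mainly restates 20 × 0.3 = 6, and that a 6-point mix shift is about one standard error of the crude trend. The adjusted trend would be imprecise and would still not isolate CQI.

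**Conclusion.** Both parts hold, with limits. The SAP sample sentence does not match the Protocol's RQ1 and needs clarifying. The effect is zero on the broad reading. On the narrow one it is s times the difference in change: ±0.5 to ±2 points under the two modest assumed cases, and up to 5 points if half of enrollees were omitted and only the included sites rose by 10. Selection on poor earlier metrics would then favor apparent improvement.

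The crude RQ1 line is valid for progress toward targets. It cannot by itself support the association aim, because site mix alone can move it.

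A reader might go further and infer that site mix did shift, or that it would flatter CQI. The documents say only that locations varied. They give no site rates or shares, so actual size and direction are unknown. Every site level, share, SD and ICC above is an assumption. The point is worth acting on mainly because the sample wording is cheap to settle. Confidence is medium.

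**What to change.** **Sample.** Replace the SAP sentence with text such as: *RQ1 uses participants at all service sites, including virtual services, with each metric's denominator as defined in Protocol Table 4 (for survey response, eligible participants). RQ2 uses, for each metric, participants at the sites that chose that metric for improvement.* If the two samples coincide, say so. This costs two sentences.

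**Site mix.** Keep the crude line for targets. Beside it, add:

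- a table of enrollees by site and period;
- one supplementary RQ1 trend per metric: a participant-level regression on enrollment time with site fixed effects (linear for dosage, logistic or linear-probability for the binary metrics). Standard errors should allow for group classes, with a small-sample correction, since uncorrected 95% intervals covered 0.90 to 0.95 in the SD 30 simulation;
- a rule, fixed in advance, for pooling sparse sites, for example by type of setting.

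State that the adjusted trend removes site mix only. It leaves change over calendar time in place and does not isolate a CQI effect.

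The programmatic data are already to be merged by client ID, so the cost is a table, three models and the modelling choices above. The main downside is imprecision. Under the assumed inputs the adjusted standard error is roughly 4 to 6 points for dosage and 5 to 8.5 for attrition and survey response, against about 5 to 8 for the crude trend. The adjusted result may also look less favorable.

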### 2. Outcomes evaluation enrollment

This study was initially approved by Solutions IRB on 03/29/2021 and has been annually reviewed and approved on 03/15/2022, 03/07/2023, and 3/11/2024. Additionally, revisions to the study were submitted as amendments and were approved on 05/17/2022, 02/15/2023, and 08/29/2023.

Participants for the program, and thus the study, are recruited primarily from community partnerships, walk-ins to Anthem Strong Families, radio and social media advertising, and word of mouth referrals.

Program service locations have varied throughout the implementation of the program but have included:

---

- Schools
  - Stephen C. Foster Elementary School
  - Herbert Marcus Elementary School
  - Burnet Elementary School
- Treatment Centers / Transitional Facilities
  - Soul's Harbor Treatment Center
  - Free Man House Transitional Living Facility
  - Shurrun's House Sober Living Facility
  - Gateway Foundation Treatment Center
- Vickery Meadow Youth Development Foundation
- Buckner Children and Family Services, Family Hope Center at Bachman Lake
- Virtual services provided via Zoom

The projected enrollment and desired sample size for the study is 800 participants. The final report will include a breakdown of the number of sites, number of staff at each site, and number of participants at each site.

To be eligible for the program, and thus the study, participants must be 1) low-income individuals, 2) at least 18 years of age, 3) with no open criminal cases (can be deferred), and 4) able to speak and understand English or Spanish.

Consent for enrollment into the evaluation happens during program orientation, prior to the start of the first primary workshop. A consent form is provided to participants, and a script is read by either the facilitator or the data manager, explaining the study activities and the potential risks and benefits. Participants sign and date the consent form and return it to the data manager, who logs the record in a consent spreadsheet on MER's secure Dropbox.

Enrollment into the study began April 22, 2021 and is estimated to conclude February 15, 2025.

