The analysis for this evaluation will be completed using Excel and the R Studio statistical software package. Trends in programmatic outcome measures will be assessed descriptively over time using graphs that show average dosage, attrition, and survey response rates by month since program start among participants who enrolled in that month. Trends in program-level (cross-site) averages will be assessed for improvements over time, and trends in site-level averages will be assessed both for improvements since program start and immediately following the implementation of targeted interventions, which will be noted on the graphs. Site-level averages will be compared across the full study time period. Assuming the continuous, rapid cycle learning and intervention of the multistep CQI process is happening as planned, average metrics are expected to improve over time and immediately following interventions.

For the secondary research question 3 analysis, a change score will be calculated for each complete case respondent using their average at program entry and their average at program exit. We will use paired sample

t-tests to assess the magnitude and significance of mean score changes among program participants in the analytic sample. For the secondary research question 4 analysis, a basic regression model will be used to determine if higher dosage of primary workshop hours is associated with higher average scores on attitudinal items. Findings are considered statistically significant based on a $p < 0.05$, two-tailed test.

Attrition

Sample attrition is not a concern for the programmatic measures assessed for RQ1 and RQ2.

For the secondary research questions, sample attrition is related to program retention, as participants can only have complete case data if they stay in the program to take their nFORM exit survey. Anthem Strong Families staff have implemented numerous strategies to increase participant retention. Retention is tracked on an ongoing basis as part of the bi-weekly CQI team meetings between Anthem and MER staff, so decreases in survey response rates or participant retention can be tracked and addressed in real time as cohorts are enrolled in the program.

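### The SAP reads site-level change right after an intervention from enrollment-month points that would average only about 2 to 4 people, so this RQ2 reading is dominated by chance

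*SAP*

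**What the plan says.** The SAP, under Analytic approach, makes the enrollment month the plotting unit, with "graphs that show average dosage, attrition, and survey response rates by month since program start among participants who enrolled in that month". The analysis is graphical: "Trends in programmatic outcome measures will be assessed descriptively over time using graphs". Program-level averages are read for improvement over time. At site level the plan goes further: "trends in site-level averages will be assessed both for improvements since program start and immediately following the implementation of targeted interventions". Interventions are marked on the graphs. Site averages are also compared over the whole study period.

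The protocol, under Outcomes evaluation enrollment, supplies the scale: "The projected enrollment and desired sample size for the study is 800 participants" and "Enrollment into the study began April 22, 2021 and is estimated to conclude February 15, 2025". It lists ten locations (three schools, four treatment or transitional facilities, two community organisations and a virtual service), introduced by "Program service locations have varied throughout the implementation of the program but have included". Participant counts by site are left to the final report.

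Neither document states a denominator for the plotted points, a minimum number per point, a rule for pooling months, or how long the period directly after an intervention lasts.

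**The concern.** RQ2 asks whether improvement differed between sites that worked on the same metric. The evidence closest to that question is what each site's graph does after its marker. If each point is the average of a handful of people, large swings occur when nothing has changed. The eye also has no means of telling a month with one enrollee from a month with fifteen unless n is shown.

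The protocol's Outcome measures section intends to judge whether targets were reached and whether improvements were large enough to matter. A chance swing could then be written up as a success at one site and a failure at another. The issue is the unit from which the post-intervention change is read, which is separate from whether a formal test is planned.

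**Working it through.** **Inputs from the documents.** 800 participants; 22 April 2021 to 15 February 2025; ten listed locations. There is no stated per-month or per-site figure to reproduce.

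**Assumptions.** Even accrual; 4 to 10 sites active at once; true attrition constant at 30% (range 20% to 40%), since no rate is given; 10 points as an illustrative improvement, since the protocol does not quantify one.

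**People per point.**
- 1,395 days / 30.44 = 45.8 months; 800 / 45.8 = 17.5 per program-month. The RQ1/RQ2 sample is limited to "participants who received services at the facilities that received CQI intervention efforts", so the program-wide count can only be lower.
- Per site-month: 17.5 / 10 = 1.7; 17.5 / 4 = 4.4.
- With ten sites and Poisson counts, exp(−1.75) = 17% of site-months are empty, so 1 − 0.83² ≈ 32% of adjacent pairs cannot be compared at all.

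**Precision of one site point.** The 95% half-width is 1.96 × √(p(1−p)/n). At p = 0.30:
- n = 4.4: about ±43 points.
- n = 1.7: about ±68 points. The normal approximation fails here, so this shows scale only.
- n = 10: ±28 points.

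**Apparent improvement with no true change.** Two adjacent months were simulated with Poisson counts, both non-empty, and the same attrition rate. Share in which attrition falls by at least 10 points:

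| Mean per site-month | 30% rate | 20% to 40% rate |
|---|---|---|
| 1.7 (ten sites) | 34% | 28% to 37% |
| 4.4 (four sites) | 38% | 35% to 40% |
| 10 | 33% | 30% to 34% |

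The 10-point threshold is not critical. By exact binomial calculation with equal n of 2, 3 and 4 and a 70% rate, a rise of at least 20 points occurs in 29%, 33% and 35% of pairs. Across rates of 50% to 90%, which would cover survey response, the range is 16% to 36%.

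**Dosage.** With an assumed SD of 25 to 35 percentage points, the half-width 1.96 × SD/√n is ±35 to ±49 at n = 2 and ±25 to ±34 at n = 4.

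**Signal against noise.** A true change from 70% to 85%, compared between one month before and one month after, would be detected with 5% to 7% power at n = 2 to 4. A two-sided 5% comparison with 80% power needs 121 people per period.

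**What pooling buys.** The half-width of a before/after difference is 1.96 × √(2 × 0.21/n), with n people on each side, for four and ten sites respectively:
- 3 months each side (n = 13.1; 5.2): ±35; ±56 points.
- 6 months each side (n = 26.2; 10.5): ±25; ±39 points.
- 12 months each side (n = 52.4; 20.9): ±18; ±28 points.

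The chance of an apparent 10-point improvement falls from 38% to about 13% with four sites and 12 months each side. With ten sites it falls from 34% to 32% with half-year windows and to 24% to 25% with 12 months.

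**Program-level trend, for contrast.** With 46 monthly points at 17.4 people and time scaled 0 to 1, the sum of squares is 4.00 × 17.4 = 69.7. The half-width of the total change is 1.96 × √(0.21/69.7) = about ±11 points.

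**The case against.** The strongest reply has four parts.

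**Per-site counts are not a document figure.** This stands. The protocol describes group classes, and its implementation section logs interventions by cohort or date. Intake in cohorts would leave some months empty and others larger, and a month point might then be close to a cohort point. The conclusion survives: at 10 people per site-month the chance of an apparent 10-point improvement is still about 33%.

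**The SAP does not define the period directly after an intervention as the next month.** Also true. A reader may average several points by eye. Three months on each side still leaves ±35 to ±56 points, and unlabelled points would be averaged by month rather than by person.

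**The analysis is descriptive, with no test.** This does not remove the problem, because the SAP states that metrics are expected to improve directly after interventions and the graphs are read for that.

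**Pooling helps little at the smallest sites.** This stands, and the fix must say so.

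Two stronger readings are tempting and are not supported. A reader might infer that RQ1 is equally weak because a program-month holds only about 17 people. But RQ1 is read from a trend over all months, which resolves roughly 11 points, and coarser bins barely alter that. A reader might also infer that the part-months of April 2021 and February 2025 anchor the improvement since program start. The SAP names no month as the reference and speaks only of trends.

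**Conclusion.** The concern holds for one reading: site-level change directly after a targeted intervention, taken from enrollment-month averages. At about 2 to 4 people per point, roughly one adjacent pair in three (34% to 38%) shows a 10-point improvement when nothing has changed. A genuine 15-point change would be almost indistinguishable from that.

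The figures rest on 800 being reached, even accrual, 4 to 10 active sites and a 30% attrition rate. The first is the protocol's projection and the rest are assumptions. The conclusion is stable over attrition of 20% to 40% and up to 10 people per site-month. It does not reach the program-level trend for RQ1 or the full-period site averages.

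**What to change.** In the SAP, under Analytic approach:

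1. Label or size every site-level point with its n.
2. For each marked intervention, report the participant-weighted average among people enrolled in a fixed window before the marker and in one after it. Give both n's and cut the window short at any other intervention at that site. Base the post-intervention reading on this summary, not on adjacent monthly points.
3. State in advance when a pooled n is too small to read, and for such sites say so rather than report success or failure.

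Keep the monthly graphs. Quarterly program-level points are optional.

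The cost is SAP wording and a regrouping of records. The Data preparation section already exports participant-level data, and the protocol already logs the site and the cohort or date of each intervention. The downsides are coarser timing of when a change began and limited help at very small sites, where 12 months each side still leaves about a 24% to 25% chance of an apparent 10-point improvement. Site priorities are set every year, so truncation may shorten some windows further.
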